#### Compensation:

Participants are compensated for the time and effort they dedicate to the study procedures. They will receive \$30 for the initial screening visit, \$50 for completing the initial abstinence/training session, \$30 for each of the weekly visits, and \$50 for the second abstinence session. In addition, participants can earn a \$100 completion bonus for attending all sessions, up to \$255 for completing EMA, and up to \$600 bonus for biochemical verification of adherence to study cigarettes (\$1235 total). Thus, compensation is provided not only for repeated laboratory visits, but also for use of study cigarettes and completion of EMA. EMA requires multiple responses throughout the day, for a period of 3 weeks, and compensation greatly improves participants' willingness to complete these repeated assessments. In addition, study cigarette use requires committed ongoing effort from participants for a period of several weeks. As such, the compensation is commensurate with the time and effort involved. The \$100 completion incentive is included because high attrition will reduce the statistical power of the study. In addition, the \$600 adherence bonus (or \$200 if participants truthfully disclose non-study cigarette use) is included to maximize compliance with study product because non-study cigarette use will compromise the ability to evaluate group differences. Compensation will be provided at each visit and weekly for EMA. Participants are free to discontinue at any time and will receive compensation for the sessions that they complete at the same rate as participants who complete the study.

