Increased Smoking of Study Cigarettes. Past two-week timeline follow-back assessed at V1 will be used to establish a baseline average of usual brand cigarettes smoked per day. Past-week timeline follow-back will be reassessed at each subsequent weekly visit, and changes in total cigarettes smoked per day relative to

baseline will be calculated. As with our prior studies utilizing investigational cigarettes, participants exhibiting  $\geq 200\%$  increase in smoking rate will be removed from the study to prevent increased toxicant exposure.

Protection of pregnant women and fetuses. Sexually active females who are not pregnant must agree to use appropriate contraception during the course of the study, and to notify the study physician if they become pregnant during the study. A urine pregnancy test will be conducted during screening and must be negative for participants to continue with the study. A second urine pregnancy test will be conducted at visit 1, prior to dispensing any study cigarettes. As such, two sequential negative pregnancy tests are required before any study cigarette administration.

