Sample size determination. Sample size was estimated using G\*Power 3.1, assuming 85% power at alpha=0.05 for detecting group by session interactions in Aim 1 (see Statistical Design and Power for additional details). For effect sizes corresponding to Cohen's d = 0.4 to 0.6, assuming a conservative estimate of the correlation between repeated measurements of 0.4, our proposed sample size of 48 will provide 90% to 99% power for detecting group by weekly session interactions (5 measurement occasions per group), and 70% to 96% power for detecting group by abstinence session interactions (2 measurement occasions per group). Importantly, power for detecting abstinence session interactions is improved (ranging from 77% to 98%) if repeated measures correlation is higher, as suggested by our preliminary data. These calculations also do not take into account the inclusion of baseline covariates that are likely to improve power.  Moreover, a loss of 33% of the sample due to VLNC non-compliance during sensitivity analyses will still yield statistical power of 96% and 78% for analyses with 5 measurement occasions or 2 measurement occasions, respectively, under a moderate scenario in which Cohen's d = 0.5and the correlation between repeated measures = 0.5. Given the increase in statistical power associated with EMA due to a) decreasing error variance,  and b) increasing the number of repeated assessments,  it is expected that sample sizes estimates determined for Aims 1 and 3 will provide ample power for detecting group differences in reciprocal smoking-pain associations in Aim 2.

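### The stated 85% power for Aim 1 holds for the abstinence interaction only from d of about 0.48 with all 48 participants completing, and no figure allows for dropout from the primary analysis

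*Combined protocol and SAP*

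**What the plan says.** The paragraph on sample size determination (Data Analysis & Statistical Considerations) says that G*Power 3.1 was used, "assuming 85% power at alpha=0.05 for detecting group by session interactions in Aim 1". Under Specific Aim 1 in the same section there are two such interactions: group by week over five visits (V1 to V5), and group by session over the two 24-hour abstinence tests.

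The inputs are given next: "For effect sizes corresponding to Cohen's d = 0.4 to 0.6", "assuming a conservative estimate of the correlation between repeated measurements of 0.4", and N=48. The stated results are:

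- Weekly interaction: 90% to 99%.
- Abstinence interaction: "70% to 96% power for detecting group by abstinence session interactions", rising to 77% to 98% if the correlation is higher (value not stated).
- After losing 33% of the sample to VLNC non-compliance in sensitivity analyses, at d=0.5 and correlation 0.5: 96% (five occasions) and 78% (two occasions).

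Design & Procedures gives 24 participants per arm, so 48 is the number randomised. Under Compensation, a completion bonus is justified because "high attrition will reduce the statistical power of the study", and participants may stop at any time. Under Risk/Benefit Assessment, participants whose smoking rate rises by 200% or more "will be removed from the study to prevent increased toxicant exposure". The text supplied gives no expected dropout rate and no inflation for it.

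**The concern.** The 85% is attached to the Aim 1 interactions as a whole, with no effect size beside it. Yet the range given for one of the two interactions begins 15 points lower. A reader who takes the 85% at face value would credit the abstinence test with power that it lacks at the lower end of the planned effect range.

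The number powered on is also the number randomised, although the plan expects that some people may leave and provides for removing others. The abstinence contrast is the more exposed of the two. It has only two occasions, and someone who misses the second contributes little to the estimate of pre-post change.

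Hypothesis 1b depends on this contrast. If it comes out null, a reader relying on 85% power could take that as evidence of no effect when the design had a substantial chance of missing one.

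**Working it through.** **Inputs.** From the sample size paragraph: alpha 0.05, d = 0.4 to 0.6, correlation ρ = 0.4, N = 48, m = 5 or 2 occasions. From Design & Procedures: k = 2 groups of 24. The G*Power module is not named; the repeated-measures within-between interaction is inferred and confirmed by reproduction.

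**Formula.** f = d/2; λ = f²·N·m/(1−ρ); df1 = (k−1)(m−1); df2 = (N−k)(m−1). Power is the upper tail of the noncentral F beyond the 5% critical value.

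**Step 1: reproduce the plan.**

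| N | m | ρ | d | λ | Computed | Stated |
|---|---|---|---|---|---|---|
| 48 | 5 | 0.4 | 0.4 | 0.04×240/0.6 = 16.0 | 90.4% | 90% |
| 48 | 5 | 0.4 | 0.6 | 0.09×240/0.6 = 36.0 | 99.9% | 99% |
| 48 | 2 | 0.4 | 0.4 | 0.04×96/0.6 = 6.4 | 69.7% | 70% |
| 48 | 2 | 0.4 | 0.6 | 0.09×96/0.6 = 14.4 | 96.0% | 96% |
| 48 | 2 | 0.5 | 0.4 | 0.04×96/0.5 = 7.68 | 77.4% | 77% |
| 48 | 2 | 0.5 | 0.6 | 0.09×96/0.5 = 17.28 | 98.3% | 98% |
| 32 | 5 | 0.5 | 0.5 | 0.0625×160/0.5 = 20.0 | 95.7% | 96% |
| 32 | 2 | 0.5 | 0.5 | 0.0625×64/0.5 = 8.0 | 78.1% | 78% |

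All eight figures reproduce; the 0.5 for the higher correlation is inferred from the match. The last two rows use 48 − 16 = 32 participants. With 48 they would be 99.6% and 92.4%.

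**Step 2: where 85% holds for the abstinence interaction.** At N=48 and ρ=0.4, power at d=0.5 (λ = 10.0) is 87.2%. Solving for 85% gives d = 0.484 at ρ=0.4 and d = 0.442 at ρ=0.5. The weekly interaction reaches 85% from d = 0.371 at ρ=0.4, so it exceeds 85% across the whole planned range.

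**Step 3: power with fewer completers.** The plan gives no rate. The assumed losses are 4/48 = 8%, 8/48 = 17% and 12/48 = 25%.

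| Completers | Abstinence, d=0.4, ρ=0.4 | Abstinence, d=0.5, ρ=0.4 | Abstinence, d=0.6, ρ=0.4 | Abstinence, d=0.5, ρ=0.5 | Weekly, d=0.4, ρ=0.4 |
|---|---|---|---|---|---|
| 48 | 70% | 87% | 96% | 92% | 90% |
| 44 | 66% | 84% | 94% | 90% | 87% |
| 40 | 61% | 80% | 92% | 87% | 84% |
| 36 | 57% | 76% | 89% | 83% | 79% |

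**Step 4: what d means here.** With two groups and two occasions, the interaction shifts each cell mean by f SD. The group difference in change is therefore 4f = 2d. Check with a t-test on change scores: SE = √[2(1−0.4)(1/24+1/24)] = √0.1 = 0.316 SD. A difference of 0.8 SD gives (0.8/0.316)² = 6.4, the λ for d=0.4 above, and 69.7% power. So d=0.4 means a 0.8 SD difference in change, and 85% power needs 2×0.484 = 0.97 SD. If d were itself the difference in change, λ at ρ=0.4 would be 0.4²/0.1 = 1.6 to 0.6²/0.1 = 3.6, and power 24% to 46%.

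**The case against.** Nothing is miscalculated or hidden. Every figure reproduces, and the 70% appears right after the 85% with its inputs. The plan does not claim 85% at every d. At d=0.5, the effect size in the scenario that it calls moderate, the abstinence test has 87% power even at the conservative correlation, and the weekly test has 90% or more throughout. The plan says its preliminary data point to a higher correlation and that covariates should help. Mixed models and multiple imputation are specified. A separate section on statistical design and power is cited but is not in the text supplied, so it may hold a dropout allowance or the d behind the 85%.

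Much of this stands. The weekly figures in Step 3 are pessimistic because mixed models use partial data. At d=0.5 and correlation 0.5, abstinence power stays at 83% or more down to 36 completers. But the higher correlation still leaves the plan's own lower limit at 77%. Screening covariates mainly explain differences between people, not variation in change, and the plan puts no number on their benefit. Modelling or imputing a missing second abstinence session restores little of the information in a two-occasion contrast. The unseen section could explain the 85%, but it would not make that figure hold at d=0.4.

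A reader might infer that every power figure assumes all 48 finish. That is not so: the 96% and 78% rest on 32 participants. That scenario is confined to non-compliance in sensitivity analyses and uses d=0.5 and correlation 0.5. At correlation 0.4, the same 32 give 52% at d=0.4 and 71% at d=0.5 for the abstinence test.

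**Conclusion.** The point holds in a limited form. For the abstinence interaction, 85% power is delivered only over the upper part of the planned effect range: from d of about 0.48 at correlation 0.4, or 0.44 at 0.5, with 48 completers. The headline figures make no allowance for dropout from the primary analysis. Under an assumed 8% to 25% loss at correlation 0.4, power falls to 66% to 57% at d=0.4 and 84% to 76% at d=0.5. These values treat non-completers as contributing nothing, which is close to true for the abstinence contrast and too harsh for the weekly one.

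The scale of d should be stated as well. The figures imply a group difference in change of 0.8 SD at the bottom of the range, which a reader would not guess from d=0.4. A reader might infer that true power is 24% to 46%. That follows only if d was meant as the difference in change, and the documents do not say so. Nor do they support a conclusion that the trial is underpowered throughout or must enrol more people. The defect is a power statement given without the conditions under which it is true.

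**What to change.** In the sample size paragraph, replace the 85% statement with wording such as: *N=48 completers gives 85% power for the abstinence interaction at d of about 0.48 (correlation 0.4), that is, a group difference in pre-post change of about 0.97 SD.* State that f = d/2 was used. Add the abstinence power at 44, 40 and 36 completers for d = 0.4, 0.5 and 0.6 (Step 3), with the assumed loss labelled as an assumption or replaced by a rate from the group's earlier studies. Say that the 33% scenario covers non-compliance and not dropout. If the cited power section already contains any of this, bring it into this paragraph.

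The change is to wording only. Enrolment, visits and analyses stay as they are. The cost is that the stated power looks less favourable.

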# **Data Analysis & Statistical Considerations**

Describe endpoints and power calculations. Provide a detailed description of how study data will be
analyzed, including statistical methods used, and how ineligible subjects will be handled and which
subjects will be included for analysis. Include planned sample size justification. Provide estimated time
to target accrual and accrual rate. Describe interim analysis including plans to stop accrual during
monitoring. Phase I studies, include dose escalation schema and criteria for dose escalation with
definition of MTD and DLT.

Hypothesis testing will be conducted using generalized mixed models, which are well-equipped to handle missing data, even when data is missing not completely at random. Multiple imputation will also be used to further address potential bias resulting from missing data.

Specific Aim 1 will examine the effects of NNCs versus VLNCs on: a) changes in cigarettes smoked per day, nicotine dependence, withdrawal symptoms and pain across the 5 weekly visits (V1 through V5), and b) pre-post intervention changes in withdrawal and pain following 24hr abstinence. For both sets of models, Group will be entered as a between-subjects factor with 2 levels (NNC or VLNC), and Session will be included as a within-subjects factor with 5 (week) or 2 (pre- vs post-intervention) levels. Baseline pain and FTCD scores, assessed at screening, will be included along with sex as covariates. We predict that the VLNC group will exhibit decreasing nicotine dependence and smoking frequency across the 4 weeks of study cigarette use, with no change for the NNC group (i.e., Group x Week interactions). Based on our prior work, we predict only a minimal increase in withdrawal during the first week of VLNC use, with no group differences in withdrawal or pain during remaining weekly visits. During 24-hr abstinence, we predict a Group x Session interaction, such that the VLNC group will exhibit pre- to post-intervention decre ases in withdrawal and pain, with no change for the NNC group. Secondary analyses will evaluate effects of abstinence, controlling for weekly changes during ad lib smoking, by including withdrawal and pain assessed at V1 (pre-intervention) and V5 (post-intervention) as time-varying covariates.

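### The Aim 1 powers correspond to differences in change of about 0.8 to 1.7 SD under the predicted pattern; at 0.4 to 0.6 SD, power is far lower than stated

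*Combined protocol and SAP*

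**What the plan says.** The sample size paragraph (Data Analysis & Statistical Considerations, Sample size determination) used G*Power 3.1, "assuming 85% power at alpha=0.05 for detecting group by session interactions in Aim 1". Its assumptions are: "For effect sizes corresponding to Cohen's d = 0.4 to 0.6, assuming a conservative estimate of the correlation between repeated measurements of 0.4". On that basis it states:

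- Five weekly visits: "our proposed sample size of 48 will provide 90% to 99% power for detecting group by weekly session interactions (5 measurement occasions per group".
- Two abstinence sessions: "70% to 96% power for detecting group by abstinence session interactions (2 measurement occasions per group", rising to 77-98% at a higher correlation whose value is not given there.
- After a 33% loss to VLNC non-compliance, with d = 0.5 and correlation 0.5, the analyses "will still yield statistical power of 96% and 78% for analyses with 5 measurement occasions or 2 measurement occasions".

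On covariates it adds: "These calculations also do not take into account the inclusion of baseline covariates that are likely to improve power". It then uses the Aim 1 and 3 estimates, together with arguments specific to EMA, to claim ample power for Aim 2.

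The Specific Aim 1 paragraph of the same section predicts that dependence and smoking frequency fall in VLNC, "with no change for the NNC group (i.e., Group x Week interactions". For the abstinence sessions it likewise predicts a pre-to-post fall in VLNC and no change in NNC. On the model it says: "Baseline pain and FTCD scores, assessed at screening, will be included along with sex as covariates".

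**The concern.** Cohen's d has a plain meaning for a difference between two means. A group-by-session interaction has no such default. G*Power asks for f, the SD of the interaction cell effects divided by the outcome SD, and the f that corresponds to a given difference in change depends on the pattern of means. The supplied text says neither which contrast d describes, nor in which SD, nor what f was entered. If f was taken as d/2, the powers belong to a much larger difference in change than a reader will take from d = 0.4 to 0.6.

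These figures justify N = 48, support the adherent-subset analysis and feed into the Aim 2 claim. A reader of a non-significant Group x Session test would overrate how well the trial could rule out a 0.4 to 0.6 SD difference.

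**Working it through.** **Inputs.** From the plan: N = 48 (24 per arm); alpha = 0.05; m = 5 or 2 occasions; d = 0.4 to 0.6; rho = 0.4; reduced sample d = 0.5 and rho = 0.5. The 33% loss gives N = 32. Assumed here: rho = 0.5 for the 77-98% pair (the paragraph says only that it is higher; 0.5 reproduces both figures), and a 16:16 split at N = 32.

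**Step 1. Reproduce the plan's figures.** For G*Power's within-between interaction with two groups, use a noncentral F with lambda = f²·N·m/(1 − rho), df1 = m − 1, df2 = (N − 2)(m − 1). Enter f = d/2. For example, m = 5, d = 0.4, rho = 0.4: lambda = 0.04 × 48 × 5/0.6 = 16, power 90.4%.

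| Case | d | lambda | Power | Plan |
|---|---|---|---|---|
| m = 5, N = 48, rho 0.4 | 0.4 / 0.6 | 16.0 / 36.0 | 90.4 / 99.9% | 90 / 99% |
| m = 2, N = 48, rho 0.4 | 0.4 / 0.6 | 6.4 / 14.4 | 69.7 / 96.0% | 70 / 96% |
| m = 2, N = 48, rho 0.5 | 0.4 / 0.6 | 7.68 / 17.28 | 77.4 / 98.3% | 77 / 98% |
| m = 5, N = 32, rho 0.5 | 0.5 | 20.0 | 95.7% | 96% |
| m = 2, N = 32, rho 0.5 | 0.5 | 8.0 | 78.1% | 78% |

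All eight agree within one point. Entering f = d or f = d/4, using alpha = 0.10, or dropping the m/(1 − rho) factor does not reproduce the set.

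**Step 2. What f means for the predicted pattern.** Let NNC be flat and let VLNC change by d times a shape running from 0 to 1. The interaction effects are half the centred shape in each arm, so f² = d² × Var(shape)/4, with the variance taken over the m occasions.

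| Shape | Var | f | Difference implied by f = 0.2 to 0.3 |
|---|---|---|---|
| Two sessions (0, 1) | 0.25 | 0.250d | 0.80-1.20 SD |
| Five visits, linear (0, ¼, ½, ¾, 1) | 0.125 | 0.177d | 1.13-1.70 SD |
| Five visits, step at V2 | 0.16 | 0.200d | 1.00-1.50 SD |
| Five visits, step at V3 | 0.24 | 0.245d | 0.82-1.22 SD |

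**Step 3. Power if d is the difference in change in single-occasion SDs** (N = 48, d = 0.4 to 0.6). For example, two sessions, d = 0.4, rho = 0.4: f = 0.1, lambda = 0.01 × 48 × 2/0.6 = 1.6, power 23.6%.

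| Shape | rho 0.4 | rho 0.5 | Plan |
|---|---|---|---|
| Two sessions | 24-46% | 27-53% | 70-96% (rho 0.4); 77-98% (higher rho) |
| Linear, 4 df | 17-35% | 20-42% | 90-99% (rho 0.4) |
| Step at V2, 4 df | 21-44% | 24-52% | 90-99% (rho 0.4) |
| Step at V3, 4 df | 30-63% | 36-72% | 90-99% (rho 0.4) |

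Simulated repeated-measures ANOVA (10,000 runs, rho 0.4) gave 23/46%, 17/34%, 21/45% and 29/62% at d = 0.4/0.6.

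**Step 4. Adherent subset** (N = 32, d = 0.5, rho = 0.5). Two occasions: 28%, against 78% in the plan. Five occasions: 20% (linear), 25% (step at V2) or 37% (step at V3), against 96%. If all 16 losses are in VLNC, the split is 24:8 and power falls to 22% (two occasions), 16% (linear) and 19% (step at V2).

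**Step 5. Difference detectable with 85% power** (N = 48, rho 0.4): 0.97 SD for two sessions. For five visits: 1.05 SD (linear), 0.93 SD (step at V2), 0.76 SD (step at V3).

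**Step 6. Possible rescues.**

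- *Change-score SDs.* A two-sample t test on change at N = 48 has 27-53% power at d = 0.4 to 0.6.
- *Higher correlation.* At d = 0.4, 70% for two sessions needs rho = 0.85. For five visits, 90% needs 0.85 (step at V3), 0.90 (step at V2) or 0.92 (linear). The paragraph gives 0.4 and 0.5.
- *Covariates.* Screening pain, screening FTCD and sex do not vary over sessions. As main effects they do not reduce the within-person error that tests Group x Session. In 20 simulated complete data sets, adding such a covariate moved the interaction t by at most 0.007.
- *Other analyses.* A V1-adjusted comparison of change over two sessions would give 32-60% (rho 0.4). A 1-df linear trend over five visits would give about 29-56% (rho 0.4). A 1-df V1-adjusted mean of V2 to V5 under a step at V2 would give 58-90%. None of these is the Group x Session test planned for Aim 1.

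**The case against.** The strongest reply is that nothing has been miscalculated: every power reproduces, and d may simply be a label for 2f. The paragraph does not say that d is a difference in change in single-occasion SDs, and it points to a Statistical Design and Power section that is not in the supplied text and may define both quantities. That stands as a limit: the lower powers are conditional on how d is read. It does not remove the problem. Whatever d was meant to be, f = 0.2 to 0.3 under the predicted pattern is a 0.8 to 1.2 SD difference in change over two sessions, and nothing supplied tells the reader so. Reading d as equal and opposite changes in the two arms gives f = d/2 for two sessions, but contradicts the predicted absence of change in NNC.

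Other objections are fair as qualifications. The five-visit figures depend on shape; a step at V3 brings the implied V5 difference down to 0.82-1.22 SD, still above 0.4-0.6. The predicted weekly decline concerns dependence and smoking frequency, not weekly pain or withdrawal. The rho of 0.5 for the 77-98% pair and the 16:16 split are assumptions, though a 24:8 split only lowers power. The covariate point holds for main effects in a linear model with complete data.

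It can also be said that no estimate or test is biased and that only wording changes. True, but the wording is the stated justification for the sample size.

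**Conclusion.** The concern holds. The printed powers are correct for f = 0.2 to 0.3. With NNC flat, they apply to a difference in change of 0.8 to 1.2 SD (two sessions) or a V5 difference of about 1.0 to 1.7 SD (five visits, step at V2 or linear). On the natural reading of d, the Aim 1 tests at correlation 0.4 have between 17% and 63% power, depending on shape and on d within 0.4 to 0.6. The adherent-subset claim is overstated in the same way. The use of f = d/2 is inferred from the exactness of the match, since the supplied text does not state f. All figures are powers for one test, not for the Aim 1 outcomes taken together. The plan's 85% target is not itself contradicted: on its own method, d = 0.48 gives 85% for two sessions at correlation 0.4.

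**What to change.** Restate the sample size paragraph in one of two ways.

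1. Define the contrast and SD unit of d, state the f entered, and recompute power for the predicted pattern, giving the correlation and the weekly shape assumed.
2. Keep the powers and add: *Powers were computed with interaction f = 0.2 to 0.3. With NNC unchanged, this corresponds to a VLNC-NNC difference in change of 0.8 to 1.2 SD (two sessions) and a V5 difference of about 1.0 to 1.7 SD (five visits, step at V2 or linear).*

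In either case, give the difference detectable with 85% power, state the correlation behind the 77-98% range, and restate the adherent-subset figures on the same basis with the assumed split between arms. Remove or qualify the covariate sentence for the Group x Session test, and do not rest the Aim 2 power claim on the uncorrected figures.

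The cost is rewording one paragraph. N, endpoints and models stay as they are; the stated power, or the stated effect size, becomes less favourable.
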